10.4.4 Retention of Documentation

All study related correspondence, patient records, consent forms, patient privacy documentation, records of the distribution and use of all investigational products, and copies of CRFs should be maintained on file.

For countries falling within the scope of the ICH guidelines, the sponsor-specific essential documents should be retained until at least 2 years after the last approval of a marketing application in an ICH region and until there are no pending or contemplated marketing applications in an ICH region or at least 2 years have elapsed since the formal discontinuation of clinical development of the investigational product. These documents should be retained for a longer period, however, if required by the applicable regulatory requirement(s) or if needed by the sponsor.

In addition, for countries not falling within the scope of the ICH guidelines, local regulatory requirements should be followed regarding the retention of clinical study documentation.

Allergan requires that it be notified in writing if the investigator wishes to relinquish ownership of the data so that mutually agreed-upon arrangements can be made for transfer of ownership to a suitably qualified, responsible person.

10.5 Labeling, Packaging, and Return or Disposal of Study Medications/Treatments

10.5.1 Labeling/Packaging

Study medication will be packaged, labeled, and supplied by Allergan or an Allergan approved labeling, packaging and distribution vendor. All study medications will be supplied in identical appearing packaging, identified as an investigational compound and will be labeled with the protocol study number and medication kit number. The label will contain information per country specific regulatory requirements and may include but is not limited to storage conditions and a caution statement regarding investigational use.

10.5.2 Clinical Supply Inventory

The investigator must keep an accurate accounting of the number of investigational units received from Allergan, dispensed to the patients, the number of units returned to the investigator by the patient, and the number of units returned to Allergan during and at the completion of the study. A detailed inventory must be completed for the study medication. The study medication must be dispensed only by an appropriately qualified person to patients in the study. The medication is to be used in accordance with the protocol by patients who are under the direct supervision of an investigator. A unit is defined as a single-dose vial.

10.5.3 Return or Disposal of Study Medications/Treatments and/or Supplies

[REDACTED]

[REDACTED] If local policy does not allow storage of used study medication vials, the site may destroy the used vials per their local policy, but must keep the kit box for the detailed inventory of the study medication.

10.6 Monitoring by the Sponsor

A representative of the sponsor will monitor the study on a periodic basis. The determination of the extent and nature of monitoring will be based on considerations such as the objective, purpose, design, complexity, blinding, size, and endpoints of the study.

Authorized representatives of Allergan or regulatory authority representatives will conduct on-site visits to review, audit and copy study-related documents. These representatives will meet with the investigator(s) and appropriate staff at mutually convenient times to discuss study-related data and questions.

10.7 Handling of Biological Specimens

[REDACTED]

Approval Date: 10-Apr-2018

Details about the handling, processing, and shipment of all biological specimens are provided in the procedure manual.

[Redacted]

10.8 Publications

[Redacted]

12.1 Glossary of Abbreviations

Term/Abbreviation	Definition
2Q8	treatment group that has 2 mg abicipar administered at baseline (day 1) and weeks 4 and 8, followed by doses at 8-week intervals through week 96
2Q12	treatment group that has 2 mg abicipar administered at baseline (day 1), and weeks 4 and 12, followed by doses at 12-week intervals through week 96
AMD	age-related macular degeneration
ANCOVA	analysis of covariance
AREDS	Age-Related Eye Disease Study
BCVA	best-corrected visual acuity
BUN	blood urea nitrogen
CFR	Code of Federal Regulations
CI	confidence interval
CIOMS	Council for International Organizations of Medical Sciences
CMH	Cochran-Mantel-Haenszel
CNV	choroidal neovascularization
CRF	case report form
CRT	central retinal thickness
eCRF	electronic case report form
DA	disc area
DSMC	Data and Safety Monitoring Committee
ETDRS	Early Treatment of Diabetic Retinopathy Study
	
EU	European Union
GCP	Good Clinical Practices
FDA	Food and Drug Administration
HIPAA	Health Insurance Portability and Accountability Act
ICH	International Council on Harmonisation
IEC	Independent Ethics Committee
IOP	intraocular pressure
IRB	Institutional Review Board
IVRS	interactive voice response system

Term/Abbreviation	Definition
IWRS	interactive web response system
ITT	intent-to-treat (population)
LOCF	last observation carried forward
MedDRA	Medical Dictionary for Regulatory Activities
MMRM	mixed-effect model for repeated measures
MP	Molecular Partners
[REDACTED]	[REDACTED]
OCT	optical coherence tomography
OU	both eyes
PDT	photodynamic therapy
PEG	polyethylene glycol
PK	pharmacokinetic(s)
PP	per-protocol (population)
PPV	pars plana vitrectomy
RBC	red blood cell
REACH	Study 150998-001
RPE	retinal pigment epithelium
rQ4	control treatment group that has 0.5 mg ranibizumab administered every 4 weeks through week 96
SD-OCT	spectral-domain optical coherence tomography
SE	study eye
SEQUOIA	Study 150998-006 (current study)
TEAE	treatment-emergent adverse event
US	United States
VEGF	vascular endothelial growth factor
WBC	white blood cell
[REDACTED]	[REDACTED]

12.2 Protocol Amendment Summary Amendment 1

Title: Safety and Efficacy of Abicipar Pegol (AGN-150998) in Patients With Neovascular Age-related Macular Degeneration

Protocol 150998-006 Amendment 1

Date of Amendment: March 2015

Amendment Summary

This summary includes changes made to Protocol 150998-006 (approved November 2014).

Following is a summary of content-oriented changes that were made to each section of the protocol, and a brief rationale for these changes. Minor editorial and document formatting revisions have not been summarized.

Section	Revision	Rationale
Title page (page 2)	Added the underlined text: “The following information can be found on FDA Form 1572 and/or study contacts page and/or Trial Master File : Name and contact information of Allergan study personnel and Emergency Telephone Numbers; name, address, and statement of qualifications of each investigator; name of each subinvestigator working under the supervision of the investigator; name and address of the research facilities to be used; name and address of each reviewing IRB; US 21 CFR 312.23 section 6(iii)b.”	FDA Form 1572 is a US-specific document and will only be collected for US study sites. Investigator information may also be found in the trial master file.
[REDACTED]	[REDACTED]	[REDACTED]

Approval Date: 10-Apr-2018

Section	Revision	Rationale
[REDACTED]	[REDACTED]	[REDACTED]
[REDACTED]	[REDACTED]	[REDACTED]
[REDACTED]	[REDACTED]	[REDACTED]
[REDACTED]	[REDACTED]	[REDACTED]
[REDACTED]	[REDACTED]	[REDACTED]
[REDACTED]	[REDACTED]	[REDACTED]

Approval Date: 10-Apr-2018

Section	Revision	Rationale
[REDACTED]	[REDACTED]	[REDACTED]
[REDACTED]	[REDACTED]	[REDACTED]
[REDACTED]	[REDACTED]	[REDACTED]
[REDACTED]	[REDACTED]	[REDACTED]
[REDACTED]	[REDACTED]	[REDACTED]

Approval Date: 10-Apr-2018

Section	Revision	Rationale
[REDACTED]	[REDACTED]	[REDACTED]

Note: Stricken text was removed and underlined text was added

12.3 Protocol Amendment Summary Amendment 2

Title: Safety and Efficacy of Abicipar Pegol (AGN-150998) in Patients With Neovascular Age-related Macular Degeneration

Protocol 150998-006 Amendment 2

Date of Amendment: April 2016

Amendment Summary

This summary includes changes made to Protocol 150998-006 Amendment 1 (approved March 2015).

Following is a summary of content-oriented changes that were made to each section of the protocol, and a brief rationale for these changes. Minor editorial and document formatting revisions have not been summarized.

Section	Revision	Rationale
Title Page (page 2)	Updated title of Allergan Signatory	Administrative change
[Redacted]	[Redacted]	[Redacted]
[Redacted]	[Redacted]	[Redacted]

Approval Date: 10-Apr-2018

Section	Revision	Rationale
[REDACTED]	[REDACTED]	[REDACTED]
[REDACTED]	[REDACTED]	[REDACTED]
[REDACTED]	[REDACTED]	[REDACTED]
[REDACTED]	[REDACTED]	[REDACTED]

Approval Date: 10-Apr-2018

Section	Revision	Rationale
[REDACTED]	[REDACTED]	[REDACTED]
[REDACTED]	[REDACTED]	[REDACTED]
[REDACTED]	[REDACTED]	[REDACTED]
Section 1	Updated to include additional support for dosing regimens used in the study	Revised language for purposes of clarification only
[REDACTED]	[REDACTED]	[REDACTED]
Section 3.1	Updated to include purpose of monitoring.	Revised language for purposes of clarification only
[REDACTED]	[REDACTED]	[REDACTED]
Section 4.5.1.1	Updated to include use of condoms as preferred method of contraception for male patients participating in the study	To specify male contraceptive measures

Approval Date: 10-Apr-2018

Section	Revision	Rationale
[REDACTED]	[REDACTED]	[REDACTED]
[REDACTED]	[REDACTED]	[REDACTED]
[REDACTED]	[REDACTED]	[REDACTED]
[REDACTED]	[REDACTED]	[REDACTED]
Section 7.3.1	Added that if non-inferiority for both abicipar arms is established, that superiority testing of abicipar over ranibizumab will be performed	Updated to reflect changes to the statistical analysis plan

Approval Date: 10-Apr-2018

Section	Revision	Rationale
[REDACTED]	[REDACTED]	[REDACTED]
Section 7.3.3	Updated to describe additional analyses if non-inferiority for both abicipar arms is established	Updated to align with FDA's comments at the end-of-phase 2 meeting
[REDACTED]	[REDACTED]	[REDACTED]
[REDACTED]	[REDACTED]	[REDACTED]
[REDACTED]	[REDACTED]	[REDACTED]
[REDACTED]	[REDACTED]	[REDACTED]
[REDACTED]	[REDACTED]	[REDACTED]
[REDACTED]	[REDACTED]	[REDACTED]
[REDACTED]	[REDACTED]	[REDACTED]

Approval Date: 10-Apr-2018

Section	Revision	Rationale
Section 10.5.3	Added the following: If local policy does not allow storage of used study medication vials, the site may destroy the used vials per their local policy, but must keep the kit box for the detailed inventory of the study medication.	Revised language for accommodating the local policy of handling the used study medication
Section 12.1	Added abbreviations for the following: ANCOVA, PDT, and PEG	Included abbreviations that were either added or not previously defined.

Note: Stricken text was removed and underlined text was added

12.4 Protocol Amendment Summary Amendment 3

Title: Safety and Efficacy of Abicipar Pegol (AGN-150998) in Patients With Neovascular Age-related Macular Degeneration

Protocol 150998-006 Amendment 3

Date of Amendment: February 2017

Amendment Summary

This summary includes changes made to Protocol 150998-006 Amendment 2 (approved April 2016).

Following is a summary of content-oriented changes that were made to each section of the protocol, and a brief rationale for these changes. Minor editorial and document formatting revisions have not been summarized.

Section	Revision	Rationale
[REDACTED]	[REDACTED]	[REDACTED]
Section 10	Updated to reflect the current template language with regards to conducting the study in accordance with applicable laws and regulations.	Administrative change.

Approval Date: 10-Apr-2018

12.5 Protocol Amendment Summary Amendment 4

Title: Safety and Efficacy of Abicipar Pegol (AGN-150998) in Patients With Neovascular Age-related Macular Degeneration

Protocol 150998-006 Amendment 4

Date of Amendment: April 2018

Amendment Summary

This summary includes changes made to Protocol 150998-006 Amendment 3 (approved February 2017).

Following is a summary of content-oriented changes that were made to each section of the protocol, and a brief rationale for these changes. Minor editorial and document formatting revisions have not been summarized.

Section	Revision	Rationale
[REDACTED]	[REDACTED]	[REDACTED]
[REDACTED]	[REDACTED]	[REDACTED]

Approval Date: 10-Apr-2018

Section	Revision	Rationale
[REDACTED]	[REDACTED]	[REDACTED]
[REDACTED]	[REDACTED]	[REDACTED]

Approval Date: 10-Apr-2018

ALLERGAN

150998-006 Protocol Amendment 4

		5.3.1 BCVA Mean Change from Baseline

		5.3.2 5.3.3 5.3.4	SD-OCT CRT Mean Change from Baseline BCVA Improvement of ≥ 15 Letters from Baseline NEI-VFO-25 Mean Change from Baseline in Composite Score	19 20 20
	6.1 \$	Study T	reatment – Exposure and Administration	
	(5.1.1	Exposure to Study Treatments	
	6.2 A	Advers	e Events	
	6	5.2.1	TEAEs of Special Interest	
8.	Subgro	oup An	alyses	35
9.	Interin	1 Analy	/ses	35
11	. Deviat	ions fro	om Protocol	
12	. Refere	nces		38
13	. Ameno	dment(s)	38

	13.1 Amendment 1	38
	13.2 Amendment 2	39
14.	Appendix A	39

List of Tables

Table 1	Definitions for Analysis Visit Windows	9

List of Figures

1. Introduction

This document describes the planned analysis that will be used for Study 150998-005 clinical study report. This randomized, parallel-group study is designed to assess the safety and efficacy of abicipar pegol (hereafter referred to as abicipar) compared with ranibizumab in treatment-naïve patients with neovascular age-related macular degeneration (nAMD).

There will be two database locks. The first database lock (referred to as primary DBL) will occur when all patients have completed the Week 52 visit, or exited earlier. The study will be unmasked to a restricted group for primary analyses.

The second database lock (referred to as final DBL) will occur when all patients have completed the study entirely (Week 104 visit) or exited early from the study.

The analysis plan will support both primary and final DBL, but some analyses will be reduced for the final DBL. For example, demographic, baseline disease characteristics, and medical history will not be re-produced at the final DBL.

1.1 Primary Study Objectives and Design

The study objectives are to assess the safety and efficacy of abicipar compared with ranibizumab in treatment-naïve patients with nAMD.

The clinical hypotheses are:

- Multiple intravitreal injections of 2 mg abicipar have an acceptable safety profile in treatment-naïve patients with nAMD
- The efficacy of at least 1 of the 2 abicipar regimens is noninferior to that of monthly ranibizumab intravitreal injections as assessed by the proportion of patients with stable vision at Week 52

This is a multicenter, double-masked, randomized, 104-week, parallel-group, activecontrolled study to evaluate the safety and efficacy of abicipar in treatment-naïve patients with nAMD. Approximately 900 patients will be randomized by region with a 1:1:1 allocation ratio to receive one of the following three treatments:

• Treatment group 2Q8: 2 mg abicipar administered at baseline (Day 1) and Weeks 4 and 8, followed by doses at 8-week intervals through Week 96

- Treatment group 2Q12: 2 mg abicipar administered at baseline (Day 1), and Weeks 4 and 12, followed by doses at 12-week intervals through Week 96
- Treatment group rQ4: 0.5 mg ranibizumab administered every 4 weeks from baseline (Day 1) through Week 96

Regions are defined primarily based on geographical locations (eg, North America, EAME [Europe, Africa, and Middle East], Asia Pacific, and Latin America). For randomization purposes, some regions are combined and the following 3 regions are used: North America, Asia, and the rest of the world. The defined 3 regions for randomization will be used for statistical analysis. Within each region, randomization to treatment groups will be stratified by baseline value for best-corrected visual acuity (BCVA \leq 55 versus > 55 ETDRS letters), central retinal thickness (CRT \leq 400 versus > 400 microns), and lesion type of choroidal neovascularization (predominantly classic versus minimally classic or occult) in the study eye.

The study design including treatment and visit schedules is shown in Figure 1 below.

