12.1 Glossary of Abbreviations..... 68

12.2 Protocol Amendment Summary Amendment 1 70

12.3 Protocol Amendment Summary Amendment 2 74

12.4 Protocol Amendment Summary Amendment 3 80

12.5 Protocol Amendment Summary Amendment 4 81

List of Tables

[Redacted]

[Redacted]

[Redacted]

[Redacted]

List of Figures

[Redacted]

[Redacted]

Approval Date: 10-Apr-2018

[figure not shown]
Protocol Summary

Study Compound: Abicipar pegol (hereafter referred to as abicipar)

Phase: 3

Study Objective:

To assess the safety and efficacy of abicipar compared with ranibizumab in treatment-naïve patients with neovascular age-related macular degeneration (AMD)

Study Design

Duration: 104 weeks participation for each patient following randomization

[figure not shown]
Study Treatment Groups and Dosage/Dose Regimen:

- Treatment group 2Q8: 2 mg abicipar administered at baseline (day 1) and weeks 4 and 8, followed by doses at 8-week intervals through week 96
- Treatment group 2Q12: 2 mg abicipar administered at baseline (day 1), and weeks 4 and 12, followed by doses at 12-week intervals through week 96

Controls:

- Treatment group rQ4: 0.5 mg ranibizumab administered every 4 weeks through week 96

The treating investigator will administer the masked² study medication by intravitreal injection into the study eye at the assigned visits.

¹ Defined as a loss of fewer than 15 letters in best-corrected visual acuity [BCVA] compared to baseline using the Early Treatment Diabetic Retinopathy Study [ETDRS] method [hereafter referred to as letters]

² To maintain masking, patients randomized to abicipar will receive a sham injection during the study visits when they are not scheduled to receive their assigned study medication. For the sham injections, the study eye of each patient will be prepared using a standard protocol as if they were to receive an intravitreal injection as defined in the procedure manual. For the sham injection, the treating investigator will press the blunt end of the syringe against the eye, mimicking an intravitreal injection.

Visit Schedule: Patients will have visits at screening, baseline (day 1), and every 4 weeks until week 104/early exit. For patients at selected sites who will have pharmacokinetic (PK) blood sampling, there will be additional visits 2 days after the baseline (day 1) and week 24, 48, and 96 visits.

Study Population Characteristics

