Abicipar pegol (hereafter referred to as abicipar) was in-licensed from Molecular Partners (MP). The drug substance (abicipar-1) was evaluated in 2 phase 1 studies; one in patients with neovascular AMD, and one in patients with diabetic macular edema.

These data support the proposed dosing regimens of both abicipar treatment arms in the phase 3 study. These abicipar treatment regimens afford the possibility to reduce the treatment burden of the number of intravitreal injections (8 or 6 abicipar intravitreal injections in Year 1 for the 2Q8 and 2Q12 abicipar arms, respectively, versus 13 for the ranibizumab arm), while maintaining the efficacy of an anti-VEGF therapy, including 3 initial doses followed by 8- or 12-week dosing intervals to assess the efficacy and safety of abicipar in a phase 3 study.

Approval Date: 10-Apr-2018

For further information, please refer to the Investigator's Brochure for abicipar.

[figure not shown]
The purpose of this study is to evaluate the safety and efficacy of abicipar (2 mg), compared to 0.5 mg ranibizumab in treatment-naïve patients with neovascular AMD.

2. Study Objectives and Clinical Hypotheses

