5.6 Treatment Regimen and Dosing

- Treatment group 2Q8: [REDACTED]

Approval Date: 10-Apr-2018

[figure not shown]
- Treatment group 2Q12: [REDACTED]
- Treatment group rQ4: 0.5 mg ranibizumab administered every 4 weeks from baseline (day 1) through week 96

Masked study treatment will be administered into the study eye by intravitreal injection (or sham treatment). One eye will be assigned as the study eye for the duration of the study. To maintain masking, patients randomized to abicipar will receive a sham injection during the study visits when they are not scheduled to receive their assigned study medication. For the sham injections, the study eye of each patient will be prepared using a standard protocol as if they were to receive an intravitreal injection as defined in the procedure manual. For the sham injection, the treating investigator will press the blunt end of the needleless syringe against the eye, mimicking an intravitreal injection.

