6.4.2 Efficacy

6.4.2.1 Best-corrected Visual Acuity

[figure not shown]
BCVA will be quantified using the ETDRS method ([AREDS Research Group, 2001](#)).

BCVA testing should precede any examination requiring contact with the study eye. BCVA should be performed following manifest refraction and completed according to the procedures outlined in the procedure manual. [REDACTED]

[figure not shown]
[REDACTED].

[figure not shown]
Approval Date: 10-Apr-2018

Approval Date: 10-Apr-2018

Approval Date: 10-Apr-2018

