2.1 Analysis Populations

The following 3 populations will be used for statistical analysis: intent-to-treat (ITT), perprotocol (PP), and safety.

The ITT population includes all randomized patients. The ITT population will be used for all efficacy analyses.

The PP population includes all randomized and treated patients who do not have protocol deviations that impact the primary efficacy variable. The PP population will be used for analyses of the primary and secondary efficacy variables. Primary considerations for PP definition include treatment compliance that would represent the intended regimen adequately.

Specifically, the PP population will include patients who

- 1. Received at least 9 study treatments (including sham) and attended at least 9 scheduled monthly visits during the first year (before the Week 52 visit), and;
- 2. Had not missed 3 or more consecutive study treatments (including sham) before the 9th study treatment, and;

3. Did not have any major protocol deviations that impacted efficacy outcomes prior to the Week 52 visit

The PP population will also include patients who discontinued from the study as a result of treatment failure without a major deviation prior to Week 52 that impacted efficacy outcomes (even if they met criteria #1 or #2 above). Patients who escaped to standard of care by meeting the protocol criteria before Week 52 and study exit are considered as treatment failures. Final determination of the PP population will be made based on masked review of the data. Detailed specification will be documented separately prior to the primary database lock.

The safety population includes all treated patients and will be used for all safety analyses.

Analyses for ITT and PP populations will be based on randomized treatment group, whereas analyses for safety populations will be as treated, ie, based on the actual treatment that the patient received.

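### Every arm is dosed at Week 48: does a Week 52 test leave the longer abicipar intervals untested, so that the plan needs an added Week 48 comparison?

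*SAP*

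**What the plan says.** SAP Section 1.1 and the Protocol Summary give the same abicipar regimens. The 2Q8 arm is dosed at baseline and Weeks 4 and 8, then every 8 weeks to Week 96. The 2Q12 arm receives "2 mg abicipar administered at baseline (Day 1), and Weeks 4 and 12, followed by doses at 12-week intervals through Week 96". Protocol Section 5.6 gives the control as "0.5 mg ranibizumab administered every 4 weeks from baseline (day 1) through week 96".

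Protocol Section 1 describes the aim as fewer injections "while maintaining the efficacy of an anti-VEGF therapy, including 3 initial doses followed by 8- or 12-week dosing intervals", and counts 8, 6 and 13 injections in Year 1 for 2Q8, 2Q12 and ranibizumab.

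The efficacy hypothesis in SAP 1.1 is non-inferiority in stable vision at Week 52. SAP 5.2.2 tests it at Week 52 with a 10% margin and a 95.1% interval. SAP 5.3.1 tests mean acuity change at Week 52 with a 5-letter margin.

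SAP 5.1 has study-eye acuity measured at every scheduled visit. SAP 2.3 assigns days 323 to 350 to Week 48 and, where several visits fall in one window, uses the last with data. Protocol 6.4.2.1 adds: "BCVA testing should precede any examination requiring contact with the study eye".

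The two documents belong to different studies. The SAP opens with "This document describes the planned analysis that will be used for Study 150998-005 clinical study report", while the protocol's glossary labels its own trial as "Study 150998-006 (current study)". The regimens and the Week 52 tests match.

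**The concern.** The case for abicipar is that vision holds over 8 or 12 weeks without an injection. The natural place to look for failure is the end of such an interval, just before the next dose. At Week 52 the ranibizumab arm is at that point and neither abicipar arm is. If vision fell late in an interval and recovered after the next injection, a Week 52 comparison could miss it and the longer intervals would look better than they are.

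A second worry concerns data handling. If someone later took Week 48 as the end-of-interval comparison, the last-value rule could substitute a reading taken after the Week 48 injection. The protocol has a possible source: for patients with PK sampling, "there will be additional visits 2 days after the baseline (day 1) and week 24, 48, and 96 visits".

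**Working it through.** **1. Dose weeks before Week 52, from the stated regimens**

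- 2Q8: 0, 4, 8, 16, 24, 32, 40, 48, which is 8 doses
- 2Q12: 0, 4, 12, 24, 36, 48, which is 6 doses
- rQ4: 0 to 48 in steps of 4, which is 13 doses

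These reproduce the protocol's counts of 8, 6 and 13, so every arm is dosed at Week 48.

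**2. Position in the interval** = weeks since last dose ÷ dosing interval

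| Visit (before any injection) | 2Q8 | 2Q12 | rQ4 |
|---|---|---|---|
| Week 48 | 8/8 = 100% | 12/12 = 100% | 4/4 = 100% |
| Week 52 | 4/8 = 50% | 4/12 = 33% | 4/4 = 100% |
| Week 104 | 8/8 = 100% | 8/12 = 67% | 8/4 = 200% |

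All three arms are at 100% together only at Weeks 24, 48, 72 and 96. Week 104 is also the end of an interval for 2Q8. The description of the timing is therefore right.

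**3. Does the test match the hypothesis?** Yes. The hypothesis names Week 52, and so do both formal tests. Each arm is nominally 4 weeks post-dose, so the arms are compared at equal time since treatment.

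By Week 48 the regimens have also been run through in full several times: five complete 8-week intervals in 2Q8 (8–16, 16–24, 24–32, 32–40, 40–48) and three complete 12-week intervals in 2Q12 (12–24, 24–36, 36–48). Lasting loss from those intervals would still be present at Week 52. SAP 5.2 also counts as failures the patients who escaped after losing 30 or more letters, with persistent fluid, at any post-baseline visit. Only a smaller, reversible dip goes unseen at Week 52, and the documents give no figure for one.

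**4. What does the plan already hold for Week 48?**

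- Study-eye acuity at that visit (SAP 5.1).
- A repeated-measures model using all data to Week 52, with visit and treatment-by-visit terms (SAP 5.3.1). It can give a Week 48 contrast directly.
- The proportion gaining 15 letters at each post-baseline visit, with between-group comparisons by the primary method (SAP 5.3.3).
- Visit windows written for by-visit efficacy analyses generally (SAP 2.3).

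Not visible: a Week 48 interval for stable vision. SAP 5.3.1 cites a Section 5.2.4.2 that is not shown, so such an analysis may exist.

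**5. How precise would that interval be?** Use Appendix A with 240 per arm, two strata of 120 (an assumed split) and 90% stable, so x = 108 per stratum.

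- p* = (108 + 2)/(120 + 4) = 0.8871
- Variance per arm and stratum = 0.8871 × 0.1129/120 = 0.000835
- Difference within a stratum: 2 × 0.000835 = 0.00167
- Two equal strata: 0.00167/2 = 0.000835, so SE = 0.0289
- Half-width = 1.9686 × 0.0289 = 0.057, or about 5.7 points (simulated mean 5.66)

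Simulated power against −10% is 94.1% with no true difference, and 87.3%, 77.0% and 63.8% at true differences of −1, −2 and −3 points. A lower limit below −10% at Week 48 would therefore not by itself show lost efficacy.

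**6. Is the pre-injection reading at risk?** The window has 350 − 323 + 1 = 28 days, of which 350 − 336 = 14 follow the Day 336 target. A PK visit at 336 + 2 = Day 338 falls inside it. But that visit is in the 006 protocol and the window rule is in the 005 SAP. The visit is described for blood sampling at selected sites, and nothing readable says acuity is measured there. At the dosing visit itself, acuity is tested before contact with the eye. What is left is an unscheduled reading after the injection, for which no frequency is given.

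**The case for a change.** The strongest argument for acting is that the addition is cheap. It would take some SAP wording, one table and one model refit, with no effect on Week 52 alpha or power. A comparison fixed before unmasking carries more weight than one chosen afterwards, and it would address the protocol's own rationale.

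Part of this stands. The Week 52 tests describe vision 4 weeks after a dose, and a report should not present them as evidence about the last weeks of a 12-week interval. Week 48 is the last visit before the primary analysis at which all arms are at the end of their interval.

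Two things weaken it. First, it asks for more information and identifies no error: the Week 52 tests are valid and no efficacy statement would depend on the new result. Second, a rule keeping the Week 48 value pre-injection would not ensure an end-of-interval value. The per-protocol set requires only that patients "Received at least 9 study treatments (including sham) and attended at least 9 scheduled monthly visits during the first year". Subject to the other criteria, a 2Q12 patient who missed Week 36 can be included and would be 48 − 24 = 24 weeks post-dose at Week 48; a 2Q8 patient who missed Week 40 would be 48 − 32 = 16. Values carried forward could come from any point in an interval.

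**Conclusion.** The concern does not hold. The timing is as described (8/12/4 weeks since last dose at Week 48 and 4/4/4 at Week 52, for 2Q8/2Q12/rQ4), but the plan as written gives a sound answer to the Week 52 question it poses. No bias in the Week 52 tests follows from the schedule, and no size can be given for late-interval waning because the documents contain no data on it. The most that is absent from the readable text is one supportive interval, with a half-width of about 5.7 points, and a label for the visit.

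This rests on nominal visit timing, on the 005 SAP and 006 protocol sharing regimens and tests (as their readable text does), and on 240 per arm with 90% stable vision for the precision figure. If the unseen SAP text already plans by-visit stable-vision intervals, even the missing item disappears; if it does not, the Week 52 conclusions are unchanged.
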